2.0 TRIAL DESIGN

2.1 Trial Design

MK-7655 (also known as relebactam) is being developed as a fixed dose combination (FDC) with imipenem/cilastatin, a BL/BLI combination (also known as MK-7655A). Throughout this protocol the combination of imipenem/cilastatin/relebactam will be referred to as IMI/REL and imipenem/cilastatin will be referred to as IMI.

This is a randomized, double-blind (with in-house blinding), active-controlled, parallel-group, multi-site trial of IMI/REL compared with colistin (in the form of colistimethate sodium [CMS]) + IMI in subjects with imipenem-resistant bacterial infection. This study will be conducted in conformance with Good Clinical Practices.

Approximately 54 subjects with imipenem-resistant bacterial infection (with colistin and IMI/REL susceptibility) will be randomized in a 2:1 ratio to the 2 blinded, randomized arms of the study, with ~36 subjects in Treatment Group 1 (IMI/REL) and ~18 subjects in Treatment Group 2 (CMS + IMI) in order to obtain a minimum of 45 subjects (15 per infection type) who meet the criteria for inclusion in the microbiological modified intent-to-treat (mMITT) population. Subjects with hospital-acquired or ventilator-associated bacterial pneumonia (HABP/VABP), complicated intra-abdominal infection (cIAI), or complicated urinary tract infection (cUTI) as a primary infection site will be eligible for enrollment. Subjects with bloodstream infections (bacteremia) secondary to HABP/VABP, cIAI, or cUTI are eligible for enrollment. Randomization into Treatment Group 1 and Treatment Group 2 will be stratified by infection type and approximately 18 subjects will be enrolled per infection type (See Section 5.4 for details). At the discretion of the Sponsor, enrollment may be stopped prior to reaching 54 total subjects if a sufficient number of mMITT subjects have been obtained. Enrollment may also be extended beyond 54 subjects at the discretion of the Sponsor for the following reasons: 1) if additional subjects beyond 54 are required to obtain the target number of mMITT subjects; or 2) if enrollment in any individual stratum has not been completed, while other strata remain open (even after a sufficient number of mMITT subjects have been obtained in those strata), until all 3 strata have reached full capacity (i.e., 15 mMITT evaluable subjects each).

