5.3 Randomization or Treatment Allocation

Randomization will occur centrally using an interactive voice response system / integrated web response system (IVRS/IWRS). There are 2 randomized treatment arms. Subjects will be assigned randomly in a 2:1 ratio to IMI/REL + placebo to CMS (Treatment Group 1; N=~36) or CMS + IMI (Treatment Group 2; N=~18), respectively. Subjects enrolled into the open-label arm (Treatment Group 3) will be provided with IMI/REL through IVRS/IWRS as well.

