8.2.4.2 Safety Analysis Populations

The ASaT population will be used for the analysis of safety data in this study. The ASaT population consists of all subjects who received at least one dose of IV study therapy. The ASaT includes non-randomized subjects in Treatment Group 3 (IMI/REL), as well as randomized subjects in Treatment Group 1 (IMI/REL) and Treatment Group 2 (CMS + IMI). Subjects will be included in the therapy group corresponding to the study therapy they actually received for the analysis of safety data using the ASaT population. Subjects who are administered incorrect study therapy for the entire treatment period will be included in the therapy group corresponding to the study therapy actually received.

At least one laboratory or vital sign measurement obtained subsequent to at least one dose of IV study therapy is required for inclusion in the analysis of each specific parameter. To assess change from baseline, a baseline measurement is also required.

Since the assessment of treatment-emergent nephrotoxicity requires serum creatinine measurements at baseline and after at least one dose of IV study therapy, subjects who have missing data at either of these time points will be excluded from the summaries/analyses of this endpoint.

Details on the approach to handling missing data for safety analyses are provided in Section 8.2.5 (Statistical Methods).

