8.2.5.2 Statistical Methods for Safety Analyses

Safety and tolerability will be assessed by clinical review of all relevant parameters including adverse experiences (AEs), laboratory tests, and vital signs.

Any analysis of safety data that involves a comparison of IMI/REL to CMS + IMI will be restricted to Treatment Group 1 and Treatment Group 2 (the randomized treatment groups). Data from Treatment Group 3 will be summarized separately using descriptive statistics.

Due to concern for potential renal toxicity of colistin, Treatment Group 1 (IMI/REL) and Treatment Group 2 (CMS + IMI) will be compared with respect to the proportion of subjects who experience treatment-emergent nephrotoxicity using the two-sided p-value from the Fisher Exact Test.

Other safety parameters will follow a tiered approach (Table 17). The tiers differ with respect to the analyses that will be performed. Safety parameters or adverse experiences of special interest that are identified a priori constitute “Tier 1” safety endpoints that will be subject to inferential testing for statistical significance with p-values and 95% confidence intervals provided for between-group comparisons. All other safety parameters will be considered Tier 2 or Tier 3. Tier 2 parameters will be assessed via point estimates with 95% confidence intervals provided for between-group comparisons; only point estimates by treatment group are provided for Tier 3 safety parameters. P-values (Tier 1 only) and 95% confidence intervals (Tier 1 and Tier 2) will be provided for between-treatment differences in the percentage of subjects with events; these analyses will be performed using the (unstratified) Miettinen and Nurminen method [78], an unconditional, asymptotic method (with the exception of treatment-emergent nephrotoxicity as described above).

Adverse experiences (specific terms as well as system organ class terms) and other safety parameters that are not pre-specified as Tier-1 endpoints will be classified as belonging to “Tier 2” or “Tier 3”, based on the number of events observed. Membership in Tier 2 requires that at least 4 subjects in at least one treatment group exhibit the event; all other adverse experiences and safety parameter will belong to Tier 3.

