The threshold of at least 4 events was chosen because the 95% confidence interval for the between-group difference in percent incidence will include zero when each treatment group has less than 4 events and thus would add little to the interpretation of potentially meaningful differences. Because many 95% confidence intervals may be provided without adjustment for multiplicity, the confidence intervals should be regarded as a helpful descriptive measure to be used in review, not a formal method for assessing the statistical significance of the between-group differences in adverse experiences and predefined limits of change.

Continuous measures such as changes from baseline in laboratory parameters that are not pre-specified as Tier-1 endpoints will be considered Tier 3 safety parameters. Summary statistics for baseline, on-treatment, and change from baseline values will be provided by treatment group in table format. Laboratory values from the Central Laboratory will be used for these analyses when available.

Table 17 Analysis Strategy for Safety Parameters

Safety Tier	Safety Endpoint [†]	p-Value	95% CI for Treatment Comparison	Descriptive Statistics
Tier 1	treatment-emergent nephrotoxicity	X	X	X
	elevated AST or ALT ≥ 3 X ULN and elevated total bilirubin ≥ 2 X ULN and alkaline phosphatase < 2 X ULN	X	X	X
	A confirmed elevated AST or ALT ≥ 5 X ULN	X	X	X
Tier 2	Any AE		X	X
	Any Serious AE		X	X
	Any Drug-Related AE		X	X
	Any Serious and Drug-Related AE		X	X
	Discontinuation due to AE		X	X
	Discontinuation due to Drug-Related AE		X	X
	Specific AEs, SOC [‡] , or PDLCs [‡] (incidence ≥ 4 of subjects in one of the treatment groups)		X	X
Tier 3	Specific AEs, SOC [‡] or PDLCs [‡] (incidence < 4 of subjects in all of the treatment groups)			X
	Change from Baseline Results (Labs, ECGs, Vital Signs)			X

[†] Adverse Experience references refer to both Clinical and Laboratory AEs.

[‡] Includes only those endpoints not pre-specified as Tier 1 or not already pre-specified as Tier 2 endpoints.

Note: SOC=System Organ Class; PDLC=Pre-Defined Limit of Change; X = results will be provided.

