		# with Nephrotoxicity in CMS+IMI group (N=15)						
		0	1(6.7%)	2 (13.3%)	3 (20%)	4 (26.7%)	5 (33.3%)	6 (40%)
# with Nephrotoxicity in IMI/REL group (N=30)	0	>0.5	0.333	0.106	0.032	0.009	0.002	<0.001
	1 (3.3%)	>0.5	>0.5	>0.5	0.101	0.036	0.012	0.003
	2 (6.7%)	>0.5	>0.5	>0.5	0.315	0.085	0.032	0.011
	3 (10%)	>0.5	>0.5	>0.5	>0.5	0.199	0.095	0.042

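### The reason given for the four-event Tier 2 cut-off does not hold at 2:1 allocation: 3 events on CMS + IMI against none on IMI/REL gives a planned 95% interval that excludes zero

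*Combined protocol and SAP*

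**What the plan says.** Section 8.2.5.2 sorts safety parameters into tiers. For items not pre-specified, "Membership in Tier 2 requires that at least 4 subjects in at least one treatment group exhibit the event"; everything else falls to Tier 3. The tiers differ in output: "Tier 2 parameters will be assessed via point estimates with 95% confidence intervals provided for between-group comparisons", whereas Tier 3 shows only an estimate for each group. On the method, "these analyses will be performed using the (unstratified) Miettinen and Nurminen method [78], an unconditional, asymptotic method".

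The cut-off of 4 is then justified by the statement that "the 95% confidence interval for the between-group difference in percent incidence will include zero when each treatment group has less than 4 events", so that such intervals would add little. No condition on group sizes is attached. The same paragraph says the intervals are unadjusted and are a descriptive aid to review, not a formal test.

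On group sizes, section 5.3 states: "Subjects will be assigned randomly in a 2:1 ratio to IMI/REL + placebo to CMS". Section 2.1 gives about 36 and about 18 subjects. Section 8.2.3.2 restricts the tiered analysis to the two randomized groups, so the open-label Treatment Group 3 does not alter the ratio. For the safety denominators, section 8.2.4.2 says: "The ASaT population consists of all subjects who received at least one dose of IV study therapy".

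**The concern.** The sentence describes a property of equal-sized groups. When one arm is half the size of the other, one event in the small arm moves the difference twice as far as one in the large arm, and so few events are needed there. If the property fails at 2:1, the plan withholds an interval it calls helpful, on the ground that it would include zero, in cases where it would not.

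At stake is the between-group display for individual AE terms, SOCs and PDLCs seen in a few CMS + IMI subjects and in no IMI/REL subjects. The plan's own planning table hints at the problem: Table 19 prints a Fisher p-value of 0.032 for 0/30 against 3/15, and the text before it says that a difference of about 3 events favoring IMI/REL falls below 0.05.

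**Working it through.** **Inputs.** Two-sided 95% level (z = 1.960) and the unstratified Miettinen-Nurminen score interval: section 8.2.5.2. Group sizes n1 = 36 (IMI/REL) and n2 = 18 (CMS + IMI): section 2.1, assuming all randomized subjects are dosed. Second case 30 and 15: Table 19. Differences are CMS + IMI minus IMI/REL.

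**Formula.** The interval excludes zero when the score statistic at zero difference exceeds 1.960. With no events on IMI/REL, b events on CMS + IMI and N = n1 + n2, the statistic (including the N/(N − 1) variance factor) reduces to

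z² = b × (n1/n2) × (N − 1)/(N − b), to be compared with 1.960² = 3.84.

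**Step 1: reproduce the plan's figures.** At equal groups, 27:27:
- b = 3: 3 × 1 × 53/51 = 3.12, below 3.84. Interval −2.3% to 28.3%.
- b = 4: 4 × 1 × 53/50 = 4.24, above 3.84. Interval 1.2% to 32.7%.

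So 4 is the right threshold for 1:1 allocation. The Table 19 entry also reproduces: for 0/30 against 3/15 the Fisher p-value is C(15,3)/C(45,3) = 455/14190 = 0.032.

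**Step 2: the trial's 2:1 allocation.**

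| IMI/REL | CMS + IMI | z² | z | 95% interval |
|---|---|---|---|---|
| 0/36 | 3/18 | 3 × 2 × 53/51 = 6.24 | 2.50 | 5.8% to 39.5% |
| 0/36 | 2/18 | 2 × 2 × 53/52 = 4.08 | 2.02 | 0.6% to 33.0% |
| 0/30 | 3/15 | 3 × 2 × 44/42 = 6.29 | 2.51 | 6.9% to 45.5% |
| 0/30 | 2/15 | 2 × 2 × 44/43 = 4.09 | 2.02 | 0.7% to 38.2% |

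All four exclude zero. Every other pair of counts below 4 includes it; for example, 1/36 against 3/18 gives −1.1% to 37.1%.

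**Step 3: dependence on the exact split.** At N = 54, solving for n1/n2:
- b = 3 needs a ratio above 3.84 × 51/(3 × 53) = 1.23. At 35:19 the interval is 4.7% to 37.8%.
- b = 2 needs a ratio above 3.84 × 52/(2 × 53) = 1.88. At 35:19 the ratio is 1.84, z is 1.94, and the interval is −0.2% to 31.6%.

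**Step 4: the other direction.** An excess on IMI/REL needs 7/36 against 0/18 (0.4% to 35.2%) before zero is excluded; 6/36 against 0/18 gives −2.2% to 32.1%. No IMI/REL count below 4 does so.

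**Step 5: how often it would matter.** The documents give no incidence for such events, so the rates here are assumptions. With true incidence 15% on CMS + IMI and 0% on IMI/REL at 36:18, the CMS + IMI count is binomial(18, 0.15):
- P(0) = 0.85^18 = 0.054 and P(1) = 18 × 0.15 × 0.85^17 = 0.170, so P(2 or more) = 0.776. The interval excludes zero in about 78% of trials.
- P(2) = 0.256 and P(3) = 0.241. The share of those trials in which the rule withholds it is (0.256 + 0.241)/0.776 = 64%. Counting only 3 against 0, it is 0.241/0.776 = 31%.

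At 15% against 2%, the first two figures become 49% and 49%. At 10% against 0% the withheld share is 82%, again about 31% counting only 3 against 0.

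**The case against.** The best defence is that little hangs on these intervals. The plan says they are descriptive and not for judging significance, so whether one excludes zero should carry no weight. The affected events are still shown by group, so a reader sees 3/18 beside 0/36. Nephrotoxicity, the comparator harm the plan singles out, is Tier 1 and gets an interval at any count, as do the two hepatic events and the six broad AE categories. All of this stands and limits the consequence. It does not rescue the sentence: the plan itself uses exclusion of zero as its reason for withholding the interval, and that premise is wrong.

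Three stronger readings are tempting and are not supported.
- A reader might infer that 2 against 0 is as secure as 3 against 0. Section 2.1 gives only approximate sizes and lets enrollment stop early or run on, and one subject's shift in the split reverses the result. Table 19 gives Fisher p = 0.106 for 0/30 against 2/15.
- A reader might infer that the rule conceals harm from IMI/REL or removes comparator harms from the report. Step 4 shows that no low-count excess on IMI/REL is affected, and Table 17 keeps descriptive statistics for Tier 3.
- A reader might take Table 19 as a direct contradiction. It is a Fisher test for a Tier 1 event, not a Miettinen-Nurminen interval; it supports the 3 against 0 case only.

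The result also depends on the planned method. A Wald interval for 3/18 against 0/36 would include zero (−0.5% to 33.9%), but the plan does not use it.

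**Conclusion.** The justification is wrong as written for this trial. The 3 against 0 case is enough to show it, and it holds at both sets of sizes in the plan and at nearby splits. The 2 against 0 case is a borderline addition that holds at exact 2:1 only.

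The practical effect is confined to a missing descriptive interval for specific AE terms, SOCs and PDLCs with an excess on CMS + IMI. The frequencies in Step 5 illustrate this under assumed incidences and are not predictions. No efficacy result, Tier 1 comparison or error rate is touched. The point deserves correction because the threshold rests on a property that the design does not have, and because correction is cheap.

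**What to change.** Delete the rationale sentence in section 8.2.5.2, or restate it for 2:1 allocation. Then do one of the following:

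1. Give the descriptive Miettinen-Nurminen 95% interval for all specific AEs, SOCs and PDLCs. This does not depend on the final group sizes.
2. Set Tier 2 membership at 2 or more subjects in Treatment Group 2, or 4 or more in Treatment Group 1. At 36:18 this captures every pair of counts for which the planned interval can exclude zero; a single CMS + IMI event against none gives z² = 36/18 = 2, well below 3.84.

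Align section 8.2.3.2 and Table 17 with the choice. The cost is wording and a few more unadjusted intervals in the AE tables, which the plan already labels as descriptive. Data collection and trial conduct do not change.

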8.2.5.3 Summaries of Baseline Characteristics, Demographics, and Other Analyses

Demographic and Baseline Characteristics

The comparability of the treatment groups for each relevant characteristic will be assessed by the use of descriptive statistics. No statistical hypothesis tests will be performed on these characteristics. The number and percentage of subjects screened, randomized, the primary reasons for screening failure, and the primary reason for study/IV study therapy discontinuation will be displayed. Demographic variables (e.g., age, gender), primary and secondary diagnoses, and prior and concomitant therapies will be summarized by treatment using descriptive statistics for continuous or categorical variables, as appropriate.

Population PK Analyses

Based on PK data and PD data obtained within this study, population PK and the relationship between PK and PD will be assessed. The results of these exploratory analyses will be included in a separate report performed by the Sponsor.

8.2.6 Multiplicity

No multiplicity adjustment is necessary as there are no statistical hypothesis tests for this protocol.

8.2.7 Sample Size and Power Calculations

This study will randomize approximately 54 subjects in a 2:1 ratio into 2 treatment groups (Group 1: IMI/REL and Group 2: CMS + IMI) in order to obtain a minimum of 45 subjects (15 per infection type) who meet the criteria for inclusion in the microbiological modified intent-to-treat (mMITT) population. An additional 5 to 10 subjects with imipenem-resistant and colistin-resistant bacterial infection will be enrolled into a third non-randomized, open-label treatment group (Group 3: IMI/REL). This is an estimation study; no formal statistical testing will be performed for the efficacy endpoints. The sample sizes planned for the study arise from logistic feasibility and are not driven by statistical considerations.

[Table 18](#) displays two-sided 95% confidence intervals for the proportion of subjects with a favorable overall response under varying assumptions for the number of successes in Treatment Group 1 (IMI/REL) and Treatment Group 2 (CMS + IMI). Estimates are provided for:

- N=5 (number of Treatment Group 2 subjects in each infection type),
- N=10 (number of Treatment Group 1 subjects in each infection type),
- N=15 (number of Treatment Group 2 subjects combined over all infection types),
- N=30 (number of Treatment Group 1 subjects combined over all infection types).

NOTE: These intervals are not symmetric around the point estimate.

Table 18 Two-Sided 95% Confidence Intervals for Favorable Overall Response

Number of subjects in population	Observed Number with Favorable overall response	(%)	Two-Sided 95% Confidence Interval ^a
5	2	40.0%	(11.6, 77.1)
	3	60.0%	(22.9, 88.4)
	4	80.0%	(36.0, 98.0)
10	4	40.0%	(16.7, 66.8)
	5	50.0%	(23.7, 76.3)
	6	60.0%	(31.2, 83.3)
	7	70.0%	(39.2, 89.7)
	8	80.0%	(47.9, 95.4)
15	6	40%	(19.8, 64.3)
	9	60%	(35.7, 80.2)
	12	80%	(54.0, 93.7)
30	12	40.0%	(24.6, 57.7)
	15	50.0%	(33.2, 66.8)
	18	60.0%	(42.3, 75.4)
	21	70.0%	(52.0, 83.5)
	24	80.0%	(62.3, 90.9)

^a 95% confidence intervals calculated with the Agresti & Coull method.

Table 19 displays several possible study outcomes for the comparison of Treatment Group 1 (IMI/REL) to Treatment Group 2 (CMS + IMI) with regard to the difference in the proportion of subjects who experience treatment-emergent nephrotoxicity. This table shows that a difference between the groups of about 3 events favoring Treatment Group 1 (IMI/REL) would be associated with a two-sided p-value that is less than 0.05.

Table 19 Fisher Exact two-sided p-values Comparing Treatment Group 1 (IMI/REL) and Treatment Group 2 (CMS + IMI) – Possible Study Outcomes

		# with Nephrotoxicity in CMS+IMI group (N=15)						
		0	1(6.7%)	2 (13.3%)	3 (20%)	4 (26.7%)	5 (33.3%)	6 (40%)
# with Nephrotoxicity in IMI/REL group (N=30)	0	>0.5	0.333	0.106	0.032	0.009	0.002	<0.001
	1 (3.3%)	>0.5	>0.5	>0.5	0.101	0.036	0.012	0.003
	2 (6.7%)	>0.5	>0.5	>0.5	0.315	0.085	0.032	0.011
	3 (10%)	>0.5	>0.5	>0.5	>0.5	0.199	0.095	0.042

8.2.8 Subgroup Analyses and Effect of Baseline Factors

To assess the consistency of the treatment effect across various subgroups, the proportion of subjects with a favorable overall response (with a nominal 95% confidence interval) within each of the randomized treatment groups (primary endpoint) will be estimated within each category of the following classification variables:

- Infection type (HABP/VABP, cIAI, cUTI)
- Gender (female, male)
- Race (e.g., White, Black, Asian)
- Ethnicity (Hispanic/Latino, non-Hispanic/non-Latino)
- Age (<65 years, ≥65 years)
- Weight (<70 kg, ≥70 kg) at study entry
- APACHE II score at study entry (≤15, >15)

In addition, the difference between Treatment Group 1 (IMI/REL) and Treatment Group 2 (CMS + IMI) will be estimated along with 90% confidence interval when the subgroups are sufficiently large (≥4 subjects in each group).

8.2.9 Interim Analyses

No formal interim analyses are planned for this study.

9.0 LABELING, PACKAGING, STORAGE AND RETURN OF CLINICAL SUPPLIES

9.1 Investigational Product

The investigator shall take responsibility for and shall take all steps to maintain appropriate records and ensure appropriate supply, storage, handling, distribution and usage of investigational product in accordance with the protocol and any applicable laws and regulations.

Clinical Supplies will be provided by the Sponsor as summarized in Table 20.

Table 20 Product Descriptions

Product Name & Potency	Dosage Form
MK-7655A, MK-7655 250 mg (Anhydrous Equivalent), IMIPENEM 500 mg (Anhydrous Equivalent) and CILASTATIN EQUIVALENT 500 mg	Powder for Constitution
IMIPENEM 500 mg (Anhydrous Equivalent) and CILASTATIN EQUIVALENT 500 mg (PRIMAXIN I.V.)	Powder for Reconstitution
Colistimethate Sodium for Injection (Equivalent to 150 mg Colistin)	Lyophilized Powder for I.V. Injection

All other supplies not indicated in [Table 20](#) above will be provided centrally by the Sponsor or locally by the trial site, subsidiary or designee, depending on local country operational or regulatory requirements.

For any commercially available product that is provided by the trial site, subsidiary or designee every attempt will be made to source these supplies from a single lot/batch number. The trial site will be responsible for recording the lot number, manufacturer and expiry date of any locally purchased product.

9.2 Packaging and Labeling Information

Clinical supplies will be affixed with a clinical label in accordance with regulatory requirements.

Subjects will receive open label, single dose vials. No kitting is required.

